Target number of participants	We anticipate to recruit 800 participants for this study over the course of 4 years

Criteria for evaluation	
Primary outcome measure(s): The primary outcome of the study is to evaluate if specific heritable arrhythmic disorders are associated with changes in selected protein distribution/expression levels at cell-cell junctions within the buccal mucosa. Our preliminary studies suggest that protein distribution/expression alterations in the buccal mucosa mirror equivalent changes that occur in the myocardium of patients with ACM. This study will evaluate the use of this "novel diagnostic tool" in individuals at risk of sudden cardiac death due to other, more common forms of arrhythmic disorders including the cardiac channelopathies. The processing approach (laboratory technique: immunocytochemistry) for protein distribution visualization has been optimized to be qualitative rather than quantitative. In this sense - each sample will be characterized by "presence" or "absence" of a specific protein at the cell-cell connections. We deem that the qualitative approach is not subject to bias and will ensure accuracy and reproducibility of the results.
 
Secondary outcome measure(s): A potential secondary outcome of the research is whether we can correlate protein distribution in the buccal mucosa with specific genotypes. Our preliminary results on the cohort of patients with ACM suggest that mutations in different genes result in different protein distribution patterns within the buccal mucosa. Being able to predict the gene bearing the disease-causing mutation will significantly reduce the time and cost of genetic sequencing. Identifying the specific gene underlying a heritable arrhythmic disorder is of pivotal importance as increasingly developing genotype/phenotype correlations help individualized risk identification and patient management.
 
Another potential secondary outcome of the research has to do with the effect changes in the patients' treatment plans may have on protein distribution. An example has to do with a protein known as Connexin43 (Cx43). Cx43 is the major gap junction protein expressed in the heart and is responsible for the electrical coupling of the cells and the smooth propagation of electricity throughout the myocardium. Cells at the buccal mucosa also express Cx43. It has been shown that patients with arrhythmic disorders show decreased distribution of Cx43 at the cell borders in their hearts and this "Cx43 remodeling" has been associated with an increased risk for arrhythmias. Our preliminary studies show that patients with ACM, as well as patients with different types of cardiomyopathy (including dilated, hypertrophic and ischemic) show Cx43 remodeling in their buccal mucosa. If a patient shows Cx43 remodeling during initial sampling and in a follow-up visit his clinical care team deems necessary to change his treatment plan (for instance, if he/she is to be started on a different anti-arrhythmic drug) we would like to study Cx43 distribution again during one of his/hers follow up visits. If the new treatment plan results in restoration of Cx43 at the buccal mucosa cell connections, and given how protein distribution in the buccal epithelium mirrors protein distribution in the heart, this finding may be an indication of successful arrhythmia management. It could thus, potentially, provide us with a non-invasive, straightforward and risk-free means to assess therapy efficacy in the future.

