This study will not have a direct benefit to the participants. However, if patients/family members decide to participate, they will help individuals at risk of sudden cardiac death (SCD) in the future. The goal of the study is to evaluate a novel, totally non-invasive, risk-free method for diagnosis of inherited heart diseases. This will aid cascade screening with the potential to diminish the burden of SCD in our society. The results of the study will also help us gain insights into mechanisms of disease pathogenesis improving our understanding and management of arrhythmic disorders. The efficacy of this approach in diagnosing and understanding ACM was published in 2016.³

Study objectives

Primary objective

The primary objective of this study is to use buccal smear samples to diagnose arrhythmic disorders. We know that heritable heart diseases affect the distribution of proteins at the cardiac intercalated disk – the area where heart cells are coupled mechanically and electronically. In the past, we have analyzed specific protein distribution patterns in heart samples to aid with patient diagnosis. Obtaining a biopsy sample from the heart, however, is an invasive, potentially risky procedure, which is not performed unless absolutely necessary and only in specialized centers. We recently showed that the buccal mucosa shows protein distribution abnormalities equivalent to those exhibited by the heart. This has provided us with a fast, inexpensive, totally risk-free way to potentially identify those individuals at risk of SCD. Moreover, the majority of the heritable heart diseases are characterized by incomplete penetrance; this means that even members of

the same family bearing the same genetic alteration may not manifest the disease to the same degree. Some family members may be “silent carriers” of the genetic change, and may thus not exhibit heart abnormalities measurable by conventional tests (such as electrocardiography and echocardiography). But they may still be at risk of SCD. It is not possible to justify a heart biopsy in a “carrier” showing no evidence of disease. The approach we are proposing, however, is giving us a totally risk-free means to cascade screen family members of individuals diagnosed with an arrhythmic disorder. This approach will also facilitate cascade screening of individuals involved in competitive, high endurance sports, who are known to be at increased risk of SCD.

Secondary objectives

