Statistical design

Statistical input in trial design

Endpoints

Primary endpoints

The primary end point will be the presence of signal for a specific protein at the junctions of the buccal smear sample. No quantification of immunoreactive signal will be performed as this approach may increase bias. Accordingly, the results for each protein stain will be categorized as “present” or “absent”.

The end point of the sub-study will be whether a protein of interest is expressed at control levels or significantly decreased levels in the presence of a mutation. Accordingly, the results for each protein examined will be categorized as ‘control’ or ‘reduced’.

Secondary endpoints

Not applicable for this study.

Sample size and recruitment

Sample size calculation

The sample size was calculated based on the size of the St. George's and satellite centres' Arrhythmia Services. The number selected constitutes only a fraction of the individuals evaluated and regularly followed at the hospitals involved and will allow us to obtain statistically significant results for each arrhythmic disorder.

Planned recruitment rate

Based on the number of patients/family members evaluated at the arrhythmic services at City St George's, University of London, we estimate that we shall be recruiting approximately 200 individuals per year over the 4 year course of the study.

Statistical analysis plan

Summary of baseline data and flow of patients

The participants will include individuals from 3 groups:

1. Patients already diagnosed with an arrhythmic disorder
2. Relatives of patients diagnosed with arrhythmic disorders to establish risk status
3. Relatives of SCD victims for risk stratification.

There shall be no randomization of the participants and no differential treatment amongst the population. All individuals enrolled will only provide a buccal smear sample.

Primary endpoint analysis

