Both for the primary study (buccal smear immunostaining) and the sub-study (buccal cell western immunoblotting) only frequencies and associations will be assessed. No complex statistical analysis is required for completion of this study. Differences between disease groups in the distribution of immunoreactive signals and levels of protein expression will be assessed in a pairwise fashion with the Fisher exact test. Bonferroni correction will be used to correct P values because of multiple comparisons as appropriate. A p value of less than 0.05 will be considered significant. SPSS 21.0 software shall be used for all analyses. This statistical analysis will be performed by [name]. If expert statistical help is required, the research team will consult medical statisticians within St. George's University of London ([name] [name]) who shall not have access to the participants' personal information.

To describe the precise methods of analysis, I shall use ACM as an example. We have previously shown that in the hearts of patients with ACM a protein known as plakoglobin is dislocated from the cell-cell junctions regardless of the underlying pathogenic mutation or even in cases where no mutation has been identified but the clinical or pathological examination are consistent with a diagnosis of ACM. We used the "presence" or "absence" of plakoglobin from the cell junctions in the buccal mucosa to predict which individuals had ACM in a blinded fashion. Of 39 patient samples obtained, plakoglobin was absent from the cell junctions in 34. It was not, however, absent in samples from patients diagnosed with other forms of cardiomyopathy including hypertrophic, dilated or ischemic cardiomyopathy. This indicated that using plakoglobin distribution in the buccal mucosa as a means to diagnose ACM had sensitivity of 87.1% and specificity of 100%.

Secondary endpoint analysis

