Regarding the secondary outcome of the analysis: patients with ACM bear mutations in genes encoding desmosomal proteins. These include desmoplakin, desmoglein2, desmocollin2, plakoglobin and plakophilin2 (PKP2). Buccal cells do not express PKP2. Instead they express a different isoform of the protein; plakophilin1 (PKP1). 15/15 ACM patients bearing mutations in PKP2 showed loss of PKP1 signal in their buccal mucosa. No patients bearing mutations in different genes showed this abnormality. Moreover, only patients bearing mutations in desmoplakin, desmoglein2 or desmocollin2 showed loss of desmoplakin signal in their buccal mucosa. Accordingly, using PKP1 distribution to predict the presence of mutations in PKP2 showed 100% specificity and sensitivity. This is a remarkable finding given how PKP1 and PKP2 are expressed by different genes localized on different chromosomes. And yet, a mutation in one

isoform expressed in one tissue affects distribution of a different isoform expressed in a different tissue. Similarly, using desmoplakin distribution to predict the presence of mutations in desmoplakin, desmoglein2 and desmocollin2 showed 100% specificity and sensitivity. We are now at a position to use the same approach in other, more common forms of arrhythmic disorders including the cardiac channelopathies.

We shall use the presence or absence of signal for specific proteins at buccal smears to:

1. predict clinical diagnosis for heritable arrhythmic disorders
2. predict the genes bearing disease-causing mutations
3. assess the effect of potential changes in treatment plan on the distribution of proteins (specifically Cx43)

We shall use the expression levels of specific proteins to establish

1. If mutations act through haploinsufficiency
2. If anti-arrhythmic medication corrects the distribution of connexin43 by increasing its production levels.

Sensitivity and other planned analyses (if applicable)

Please see explanation above

Interim analysis

If following the first year of the study, it appears that we are unable to predict "arrhythmic status" using such samples, we shall stop recruiting patients with cardiac channelopathies and will only focus on patients with cardiomyopathies, where the correlation is already proved

Committees involved in the trial

A trial management group (TMG) will be in place throughout the duration of the study

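### The primary objective is diagnosis, but the only pre-specified inferential test is between-group association, so a clinically weak marker can be declared significant

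*Combined protocol and SAP*

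**What the plan says.** Under Study objectives, Primary objective: "The primary objective of this study is to use buccal smear samples to diagnose arrhythmic disorders". The intended use described there includes cascade screening of relatives who may be silent carriers.

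The synopsis (Criteria for evaluation) words the primary outcome differently, as to "evaluate if specific heritable arrhythmic disorders are associated with changes in selected protein distribution/expression levels at cell-cell junctions within the buccal mucosa".

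Under Statistical design, Primary endpoints: "The primary end point will be the presence of signal for a specific protein at the junctions of the buccal smear sample", scored present or absent.

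Under Primary endpoint analysis, "only frequencies and associations will be assessed. No complex statistical analysis is required for completion of this study". Differences between disease groups "will be assessed in a pairwise fashion with the Fisher exact test", Bonferroni correction applies where appropriate, and "A p value of less than 0.05 will be considered significant". The same section then gives an ACM example, introduced as showing the exact method. Plakoglobin was absent in 34 of 39 patients and not absent in other cardiomyopathies, and the section concludes that the approach "had sensitivity of 87.1% and specificity of 100" per cent.

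The list of uses under Secondary endpoint analysis includes to "predict clinical diagnosis for heritable arrhythmic disorders", with no statistic attached. The sample-size section justifies the 800 participants by clinic size and by the expectation of significant results for each disorder. The interim rule turns on whether arrhythmic status can be predicted, with no measure of prediction named.

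**The concern.** A Fisher P value shows that two frequencies differ. It does not show how often the smear classifies a person correctly. Where diagnosis is the question, the deciding quantities are the proportion of affected people the smear detects and the proportion of people without that disorder it leaves negative, each with its uncertainty.

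Under the plan as written, a protein can be reported as significant for a disorder when most patients with that disorder have a normal smear. That would be a poor basis for the stated purpose of finding relatives at risk of sudden death. The plan also does not say which protein or pattern makes a smear positive for Long QT syndrome, Brugada syndrome or catecholaminergic polymorphic ventricular tachycardia, and the laboratory section allows further protein targets to be added during the study. A positivity rule could therefore be settled after the results are known.

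**Working it through.** **1. The plan's own figure.** Sensitivity in the ACM example: 34/39 = 0.8718, which the plan truncates to 87.1%. The exact (Clopper-Pearson) 95% CI is 72.6% to 95.7%. The 100% specificity cannot be checked, because the number of non-ACM samples is not given. There is no power or precision calculation to reproduce. The total is 200 per year × 4 years = 800.

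**2. Number of tests.** The laboratory section names four antibodies (plakoglobin, Cx43, desmoplakin, PKP1).
- Six disorders are named under Screening assessments: 6 × 5 / 2 = 15 pairs, and 15 × 4 = 60 tests.
- Adding cardiac sarcoidosis from the inclusion criteria gives seven: 7 × 6 / 2 = 21 pairs, and 21 × 4 = 84 tests.

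The plan does not state a number. The Bonferroni limits are 0.05/60 = 0.00083 and 0.05/84 = 0.0006.

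**3. Assumptions.** Group sizes, rates of signal loss and prevalence are assumed, because the documents give none. Tests are two-sided, since sidedness is not stated. Sensitivity is the proportion with absent signal in the disorder group. Specificity is 1 minus that proportion in the comparison group.

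**4. Can a weak marker pass?**

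| Absent, disorder vs comparison | Fisher P | Corrected P | Sensitivity | Specificity |
|---|---|---|---|---|
| 35/100 vs 10/100 | 3.4e-5 | × 84 = 0.003 | 35% (CI 26 to 45%) | 90% |
| 53/133 vs 27/133 | 0.00077 | × 60 = 0.046 | 39.8% | 79.7% |

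The 133 per group is 800/6 with an equal split. That is generous, because the 800 include relatives. In the second row the positive likelihood ratio is 0.398/0.203 = 1.96, and about 60% of affected people are missed. With 84 tests instead of 60, 54 versus 27 (40.6%) is needed.

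**5. Range.** With 20% loss in the comparison group and 60 tests, the smallest significant sensitivity is 54% at 50 per group (27 vs 10) and 35.5% at 200 per group (71 vs 40). With no loss in the comparison group, 11/133 (8.3%) is enough.

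**6. Predictive value.** PPV = sens × prev / [sens × prev + (1 − spec) × (1 − prev)]. For 35% and 90% at an assumed prevalence of 10%: 0.035/(0.035 + 0.09) = 28%. At 5% prevalence it is 16%, and at 50% it is 78%.

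**The case against.** The best counter-argument is that accuracy is already in the plan. The ACM example sits inside the Primary endpoint analysis, is presented as the method, and ends in sensitivity and specificity. The planned frequencies of absent signal by group would also yield both quantities by simple division. This stands to the extent that a reader might infer that accuracy is missing altogether, which is not so. But the example reports a past result for one protein in one disease. It sets no interval and no positivity rule for the other disorders, and does not say that accuracy decides anything.

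Second, the synopsis words the primary outcome as association, and the Fisher test fits that wording. This is true, and it means the documents do not agree on the primary question. The Primary objective section is nevertheless explicit that the aim is diagnosis.

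Third, Bonferroni correction protects against trivial differences. It raises the bar but does not close the gap, as the table shows. It does rule out some tempting illustrations: 20/100 versus 8/100 gives P = 0.024, but 0.024 × 15 is about 0.35 for 15 pairs alone.

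A reader might also infer that diagnosis has been demoted because predicting it is listed under Secondary endpoint analysis. The position of that list shows little. It gathers the uses of both assays, and the plan elsewhere says that secondary endpoints do not apply.

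**Conclusion.** The concern holds in this form: the objective is diagnosis, the only pre-specified inferential test is association, and accuracy is illustrated from past data but not set up as the analysis that answers the question. Under the assumed group sizes and loss rates, a marker detecting 35% to 40% of affected people is significant after correction for 60 to 84 tests. Larger groups or a low loss rate in the comparison group bring the figure lower.

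A reader might go further and infer that a smear with no diagnostic value could meet the primary endpoint. The documents do not support that. A significant difference in the expected direction implies some discrimination (a likelihood ratio of 3.5 in the 35% versus 10% case). The endpoint is a present-or-absent reading of each sample, and the plan states no formal success criterion to be met. Nor do these figures predict what the study will find: they show only what the rule would allow.

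**What to change.** In the Primary endpoint analysis, make the primary analysis, for each disorder:

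- **Positivity rule:** which protein or pattern counts as a positive smear, written and dated before that disorder's smear results are compared with diagnoses.
- **Sensitivity:** in participants with that clinical diagnosis, with an exact 95% CI.
- **Specificity:** in participants with a different established diagnosis, with an exact 95% CI. The ACM example already uses this kind of comparison.
- **Undiagnosed relatives and carriers:** reported separately. Some may be silent carriers whom the smear is meant to detect, so counting them as unaffected would turn correct positives into false positives.

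Base any claim that a marker is diagnostic on these estimates and intervals, not on the P value, and keep the Fisher tests as supportive. For protein targets added during the study, label accuracy results exploratory unless the rule was fixed beforehand. Align the synopsis primary outcome with the objective.

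No additional samples are needed, because the present-or-absent readings are unchanged. The cost is that claims become less favourable than a P value or a bare percentage, and intervals will be wide for small groups: 44/50 (88%) gives 75.7% to 95.5%, and 116/133 (87.2%) gives 80.3% to 92.4%. Rules for the channelopathies also have to be written, and until they are, those accuracy results remain exploratory.

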If seen at the hospital, the study participants will just be asked to open their mouth. A study team member will rub a soft brush a few times at the inside of their cheek and smear the brush on a microscopy slide. The slide will be sprayed with 70% ethanol to preserve the material and taken to the research laboratory. The patient will have a total of 6 smears taken (3 from each cheek). For the majority of the patients, only a single sampling will be enough which will take place during one of their regular follow-up appointments at the cardiology clinic or using the at-home kit. There is no pain and no discomfort associated with the procedure and it lasts only a few seconds. In selected cases, however, if for instance we want to use the buccal smear to evaluate the effect of a change in medical treatment on protein distribution, the patient might be asked to provide the study team with another sample, again during one of his scheduled regular follow-up visits or using the same self-sampling kit at home. If the at-home kit is being used, the patient will be asked to obtain their own buccal smear samples using the materials provided and mail the slides back to City St George's, University of London.

Exfoliated buccal mucosa cells have been used as a source of material for various genetic tests and in studies of oral cancer but their use in studies of cardiovascular disease has been limited. Previous applications have included analysis of telomere length in buccal cells from patients with ischemic heart failure and measurements of intracellular magnesium levels in patients undergoing radiofrequency catheter ablation for atrial fibrillation. To the best of our knowledge, our study published at *Circulation Arrhythmia and Electrophysiology* 9(2) in 2016, was the first analysis of buccal mucosa cells in patients with a heritable form of heart disease.³ This analysis included 39 patients diagnosed with ACM, a primary myocardial disease characterized by an unusually high burden of arrhythmias and SCD as well as 15 carriers of disease-causing mutations without overt disease manifestation. In a subsequent analysis (unpublished data), 55 additional individuals affected by ACM were sampled and the positive predictive value of our approach in diagnosing the disease was 91.9%. Although highly arrhythmogenic, ACM is a

[figure not shown]

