All participants that are screened for inclusion into the study must be entered onto the Sponsor screening log JREOLOG0001 and will be assigned a unique study sequential number. Participants will be considered eligible for enrolment into this trial if they fulfil all of the inclusion criteria and none of the exclusion criteria as defined below.

Eligible participants will be entered onto the Sponsors Subject ID log JREOLOG0002 and assigned a unique study specific Identification number in a pre-agreed format in accordance with Site identifier and next sequential numerical value e.g. SG001

Inclusion criteria

- Participants will include patients diagnosed with a heritable arrhythmic disorder (including arrhythmogenic, hypertrophic and dilated cardiomyopathy, cardiac sarcoidosis as well as cardiac channelopathies; Long QT syndrome, Brugada syndrome and catecholaminergic polymorphic ventricular tachycardia).
- Family members of victims of SCD evaluated at the same clinic for risk assessment and diagnosis. These groups include both individuals with clear disease manifestation (termed "affected") as shown by conventional diagnostic approaches (electrocardiography, echocardiography, cardiac MRI, Holter monitoring) as well as potential carriers of disease-causing mutations who, however, may not/not yet manifest any overt sign of cardiovascular abnormalities (termed "carriers"). These are typically family members of probands diagnosed with a heritable arrhythmic disorder or family members of a sudden cardiac death victim.
- All individuals that fall in the above categories will be included regardless of their management (medication, devices, and surgical procedures).
- Individuals with co-existing conditions will also be included and their medical history will be taken into account when interpreting the results of the immunohistochemical or Western immunoblotting analysis.
- Adult individuals (>18 years of age).
- Pregnant women will be included as the approaches used is not in any way harmful or uncomfortable.
- All individuals must have provided the study team with a signed informed consent in order to participate in the study.

Exclusion criteria

- Children under 18 years of age
- Individuals lacking decisional capacity.
- Individuals with non-heritable, non-arrhythmic cardiac disorders (such as ischemic heart disease or inflammatory disorders).

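### For the buccal-smear endpoint the plan designates no unaffected comparator, so it need not yield a false-positive rate in unaffected relatives

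*Combined protocol and SAP*

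**What the plan says.** - **Purpose.** Section 5.1 makes diagnosis the primary objective and presents the smear as a "totally risk-free means to cascade screen family members of individuals diagnosed with an arrhythmic disorder", including silent carriers.
- **Analysis.** Under Statistical design, Primary endpoint analysis, "only frequencies and associations will be assessed". Then: "Differences between disease groups in the distribution of immunoreactive signals and levels of protein expression will be assessed in a pairwise fashion", using Fisher's exact test, Bonferroni correction as appropriate and a 0.05 threshold. The term disease groups is not defined.
- **Worked example**, offered in the same section to show the method. Plakoglobin was absent in 34 of 39 patients with arrhythmogenic cardiomyopathy (ACM). "It was not, however, absent in samples from patients diagnosed with other forms of cardiomyopathy including hypertrophic, dilated or ischemic cardiomyopathy". From this the section reports 87.1% sensitivity and 100% specificity. Section 7.2 excludes from the present study "Individuals with non-heritable, non-arrhythmic cardiac disorders (such as ischemic heart disease or inflammatory disorders".
- **Participants.** The three analysis groups are diagnosed patients, "Relatives of patients diagnosed with arrhythmic disorders to establish risk status", and relatives of sudden cardiac death (SCD) victims. The two relative groups are defined by kinship, not disease status. Section 10.1 admits relatives whether or not disease is apparent.
- **Pilot.** Section 6.2 says the published series also had "15 carriers of disease-causing mutations without overt disease manifestation". The worked example gives no result for them.
- **Year-1 decision.** Interim analysis: "If following the first year of the study, it appears that we are unable to predict" arrhythmic status, recruitment of channelopathy patients stops. No comparator is given.

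**The concern.** Tests between disorders serve differential diagnosis: they ask whether one disorder's smear differs from another's. Screening a relative asks whether an abnormal smear separates people with disease from people without it. That needs the frequency of abnormal smears in unaffected people, and the plan requires no such estimate.

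Two things are at stake. First, section 10.4 lets the care team contact a participant whose self-obtained sample looks abnormal. Without a false-positive rate there is no basis for reading such a result in a relative with no other sign of disease. Second, a marker that changes in every disorder could be useful for screening and yet look uninformative in every planned test. The synopsis (section 3) reports Cx43 remodelling in ACM and in dilated, hypertrophic and ischemic cardiomyopathy, so Cx43 may be such a marker, although no rates are given.

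**Working it through.** **1. The plan's own figures.** Sensitivity is 34/39 = 0.8718. The plan prints 87.1%, which is truncated; rounded it is 87.2%. The exact 95% interval is 72.6% to 95.7%. The 100% specificity cannot be reproduced because the number of comparison patients is not given. All the comparators named are diseased.

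**2. Is an unaffected comparator designated anywhere for the smear?**

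| Place | What it offers | Unaffected smear comparator? |
|---|---|---|
| Primary endpoint analysis | Pairwise tests between disease groups | No |
| Worked example | Specificity against other cardiomyopathies | No; diseased comparators |
| Secondary endpoint analysis | Smear used to predict clinical diagnosis | Not stated |
| Summary of baseline data | Relatives grouped by kinship | No |
| Section 7.1 | Affected relatives distinguished from potential carriers | Status described, no analysis role |
| Section 10.1 | Relatives enrolled with or without disease | People available, not designated |
| Section 6.2, pilot | 15 mutation carriers; 91.9% positive predictive value, described for 55 further affected people | No |
| Section 14.2.1, sub-study | A control category for expression level | No; Western blot only, source undefined |

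**3. A marker lost equally in every disorder.** Take assumed data. With loss in 87/100 of one disorder and 87/100 of another, Fisher's p = 1.0. The same 87/100 against 0/100 unaffected people gives p of about 8 × 10⁻⁴³. By full enumeration, with 85% loss in both groups at two-sided 0.05, the planned test rejects in 2.0% (20 per group), 2.4% (38) and 3.3% (100) of studies. Any valid test of no difference between disorders behaves this way. The point is that it answers a different question.

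**4. How much depends on the missing rate.** Positive predictive value (PPV) = s·p / [s·p + (1 − spec)(1 − p)], where s is sensitivity and p the proportion of relatives affected. For illustration s = 34/39, which comes from diagnosed ACM patients rather than relatives. Specificity and p are assumed.

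| Specificity | p = 10% | p = 25% |
|---|---|---|
| 100% | 100% | 100% |
| 99% | 90.6% | 96.7% |
| 95% | 66.0% | 85.3% |
| 90% | 49.2% | 74.4% |

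For example, 0.8718 × 0.10 / (0.8718 × 0.10 + 0.10 × 0.90) = 0.0872/0.1772 = 49.2%.

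**5. What an unaffected group of size n would give.** If no smear is abnormal, the exact lower 95% limit for specificity is 0.025^(1/n): 83.2% for n = 20, 94.0% for n = 60 and 96.4% for n = 100. If 6 of 60 are abnormal, specificity is 54/60 = 90%, with limits 79.5% and 96.2%.

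**The case against.** The best defence is that the plan is less bare than its one named test suggests.

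- The synopsis describes basic, correlational science, and its primary outcome is whether specific disorders are associated with protein changes. Tests between disorders address part of that.
- The worked example proceeds by blinded prediction and then sensitivity and specificity. The Secondary endpoint analysis carries the same approach forward.
- Section 7.1 separates affected people from potential carriers, and the data collection form (section 25) records diagnosis and mutation status, so affected status is largely identifiable.
- A summary by frequencies and associations leaves room to tabulate relatives, and disease groups could be read loosely enough to include them.
- Section 12.3 says findings may only indicate a propensity, and contact under section 10.4 is discretionary.

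All of this stands as a limit on the point. A reader might infer that the study enrols no unaffected people, that specificity will not be calculated at all, or that the sub-study has no controls. The documents do not support those readings: section 10.1 admits relatives without disease, specificity is implied, and the sub-study has a control category, though its source is undefined.

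The defence does not supply the comparator. The only specificity demonstrated is disease against disease, and one of those comparators, ischemic cardiomyopathy, falls under an exclusion here. Tabulating relatives is permitted but not required. Choosing the reference group after the results are known would lose the benefit of pre-specification.

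**Conclusion.** The point holds for the buccal-smear endpoint. Followed as written, the plan need not estimate the false-positive rate in unaffected relatives, which its screening use depends on, and its named test would not flag a marker lost about equally across disorders. This should be corrected before analysis.

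The gap is one of specification and of precision for specificity. The target of 800 (200 a year for 4 years) is not shown to be too small. A reader might also infer that false positives are common. Nothing in the documents shows that, and if the pilot's 100% specificity carried over to relatives, the PPV would be 100% throughout.

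The textual finding rests on no assumption beyond the natural reading of disease groups as groups of patients. The loss rates, group sizes, specificities and prevalences above are assumptions for illustration. The exact limits treat relatives as independent; several relatives from one family would make them somewhat optimistic.

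**What to change.** In the Primary endpoint analysis:

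1. For each disorder and protein, compare diagnosed patients with clinically unaffected relatives of the kind section 10.1 already admits. Report sensitivity and specificity with exact 95% confidence intervals.
2. Define the reference group in advance. The preferred choice is relatives who tested negative for the family's known mutation. Report separately unaffected relatives who are mutation-positive, untested, or from families with no known mutation.
3. Use one pre-specified sample per person, the first, because section 10.4 plans repeat sampling.
4. Show Cx43 results by anti-arrhythmic medication, because section 10.4 says effective treatment restores its distribution and section 7.1 enrols people whatever their medication.
5. Keep the tests between disorders for differential diagnosis.
6. Base the year-1 judgement of arrhythmic status on the new comparison.
7. On the data collection form (section 25), expand the mutation item to separate tested negative, not tested, and no family mutation known.

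This group should not be assumed to supply the sub-study's control level. That would need new on-site toothbrush samples and separate consent (sections 6.1, 9.1 and 10.3).

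**Cost.** A protocol amendment with sponsor and ethics committee approval, and one form change. The extra comparisons also enlarge the Bonferroni count: the seven disorders of section 7.1 and four proteins of section 10.5.1 give 7 × 4 = 28. The main drawback is the reference group's unknown size. Only families with a known mutation contribute to the preferred group, section 8 recruits people regularly followed up and thought to be at risk, and completion is due on 30/06/2026. Even a small group would give an interval where the present plan requires none.
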